Last Updated: 2.24.2023

ARENA LABS - IMPROVING CLINICIAN WELL BEING

IRB00090882

NCT05653700

IRB Approval Date: 03.01.2023

Atrium Health | Arena Labs Research Protocol

Project Title

The effect of an asynchronous coaching platform on measures of physiological resilience, professional fulfillment, burnout, self-valuation, and overall satisfaction in Atrium Health Sanger Heart and Vascular Institute Surgery, Emergency Department, and Pulmonary Critical Care Physicians and Advanced Practice Providers.

Principal Investigator and Co-Investigator Information

Principle Investigator: [name]

Research Question/Hypothesis

What is the effect of educational content; data feedback and monitoring; and tailored coaching touchpoints provided through an asynchronous coaching platform on measures of physiological resilience, professional fulfillment, burnout, self-valuation, and overall satisfaction in full time clinical providers?

Objectives

The primary objective of this study will be to determine the efficacy of the asynchronous performance coaching platform, Arena Strive at changing measures of physiological resilience, professional fulfillment, burnout, and self-valuation in full time clinicians. The anticipated **primary outcome** will be an improvement in measures related to clinician resilience including self-reported professional fulfillment and self-valuation; factors measured by the WHOOP biometric device: Heart rate variability (HRV), resting heart rate (RHR), time spent in bed, sleep quality, sleep consistency, reduction in "sleep debt"; and a reduction in burnout. Expected **secondary outcomes** include an overall high level of self-reported acceptance, satisfaction, and feasibility of the Arena Strive Platform.

- Primary outcome: Increases in physiological and self-reported measures of resilience / decreases in burnout measures.
- Secondary outcome: Feasibility, acceptance, satisfaction of Arena Strive platform

Background to Research Questions

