Throughout the 12 week intervention period, **participant engagement** within the Arena Strive app will be collected including data points relating to videos/audio watched or listened to, content favorited, or user activities completed. Modifiable activities collected via the Arena Strive Platform include light exposure, light restriction, sleep hygiene, meal timing, and activation and deactivation techniques (yoga nidra, physiological sigh, super O2 breathing).

Self-reported data will also be collected relating to the participants ability to adapt to stress, rest and recover from stress, and self-awareness around these two constructs. WHOOP data, engagement within the Arena Strive app, and self-reported stress adaptability, rest and recovery, and self-awareness will be collected continually throughout the intervention period. The additional self-reported outcomes: professional fulfillment, burnout, self-valuation, and overall satisfaction will be collected by means of an in-app survey at key benchmark moments throughout the intervention period: once at intervention start, again at week 6 following the first phase of the Arena Strive intervention, then again at week 12 following the completion of the experimental intervention period. Participants in the control cohort will follow this same time frame with respect to self-reported surveys. All self-reported data within the control cohort will be collected via identical surveys hosted on Typeform, the web-based surveying platform.

The experimental intervention, 'Arena Strive', will be conducted through the Arena Strive app, self-described as "Healthcare's First Performance Coach". This second-generation platform provides frontline clinicians with a comprehensive journey to access the tools, training, and technology used by other high-pressure fields to increase performance and enhance resilience. Strive uses a dynamic, interactive content platform to bring frontline clinicians the lessons learned, tools, and tailored instruction of world-class performers from elite military, professional athletes, and creative performers. The design will test the effect on measures of professional fulfillment and burnout; self-valuation; satisfaction; and feasibility in full-time NHS clinicians.

Intervention

The experimental intervention employed in this study will be a 12-week, multi-phased approach involving asynchronous learning and coaching experience (6 weeks), and exploration phase (6 weeks).

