Participants sought for this study will include full time Physicians and Advanced Practice Providers employed by Atrium Health Sanger Heart and Vascular Institute, Surgery, Emergency Department, and Pulmonary Critical Care. Investigating this special subject population will allow the study team to address with the greatest accuracy the effects of the proposed intervention on the unique workforce at Atrium Health. The maximum number of subjects sought for this study is 100; with a 2:1 randomization ratio with 2/3 receiving the experimental intervention, and 1/3 receiving no intervention to act as an inactive control.

Note: The employees who volunteer for participation but are assigned to the control condition will be given the opportunity to participate in the exact same program at the completion of the trial with the experimental group. Those employees who take this opportunity can then serve as an internal replication of the findings with the experimental group.

All Participants must meet the following Inclusion/ Exclusion Criteria. Criteria points will be self-reported and acknowledged by the participant.

Key Inclusion Criteria:

- Employed full time by an Atrium Health affiliated entity
- Age 18+
- Willing and able to give written informed consent for study participation.
- Healthcare workers working ≥ 36 hours of clinical duties/week.
- Willingness to wear WHOOP and keep it charged for the entire duration of study.
- Have a smart phone for pairing with WHOOP and the Arena Strive platform.

Key Exclusion Criteria:

- Current diagnosis of a sleep-related breathing disorder including obstructive sleep apnea not being treated (with or without continuous positive airway pressure (CPAP) treatment)
- Circadian rhythm sleep-wake disorders
- Narcolepsy
- Recurrent isolated sleep paralysis
- Restless legs syndrome
- Periodic Leg Movement Disorder
- Comorbid nocturia or other conditions (eg. benign prostatic hyperplasia) resulting in frequent need to get out of bed to use the bathroom during the night (≥ 3 times per night average)
- Atrial Fibrillation
- COPD other than mild, pulmonary fibrosis or severe chronic lung disease
- Sleep apnea or undergoing treatment for a sleep related illness

Last Updated: 2.24.2023

- Lack of availability of iPhone or Android device
- Part-time clinical duties

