Participant Consent: All participants involved in this study will be required to provide written consent to participate. Participants will be asked to consent to the collection of self-reported data provided through in-app and digital surveys as well as biometric data collected through the WHOOP device. A copy of the written consent form is included in the appendix. Spanish language consents will be made available upon request.

Equipment/Supplies/Services

All equipment, services, and supplies related to the study intervention will be provided by Arena Labs, and WHOOP. All equipment, services, and supplies related to the recruitment of study participants will be provided by the Atrium Health team.

Data Collection

All study data will be collected via an in-app or online survey, through app interactions, or through the WHOOP wearable biometric device. Data collection for the control cohort will mirror that of the experimental group in both frequency and content with a select few exceptions. Control cohort participants will not receive questions relating to feasibility and satisfaction, and self-reported data will be collected via online surveys hosted on Typeform. A breakdown of the primary and secondary outcome variables are summarized below.

		Outcome Variable	Instrument	Collection Method
Primary Outcomes	Self Reported	Professional Fulfillment & Burnout	Stanford Professional Fulfillment Index (PFI)	Onboard, midpoint, and exit Survey
		"Gold standard" for measuring burnout	Maslach Burnout Inventory (MBI)	Onboard, midpoint, and exit Survey
		Self Valuation	Stanford Self Valuation Scale	Onboard, midpoint, and exit Survey
	Biometric Data	HRV	WHOOP Strap	Continuous
		SWS %	WHOOP Strap	Continuous
		REM %	WHOOP Strap	Continuous
		RHR	WHOOP Strap	Continuous
		Awake Time	WHOOP Strap	Continuous
		Light Sleep Duration (%)	WHOOP Strap	Continuous

		Sleep Disturbances	WHOOP Strap	Continuous
		Sleep Debt	WHOOP Strap	Continuous
		Sleep Consistency	WHOOP Strap	Continuous
Secondary Outcomes	Self-reported	Satisfaction	Client Satisfaction Questionnaire-8 (CSQ-8)	Exit Survey
		Feasibility/Adherence	NA	In-app Survey & app engagement

Data Analysis

- We will use t-tests in SPSS to compare the primary outcome measures across the experimental and control groups.

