- We will also test for dose effects in the experimental condition via a series of correlational analyses that estimate whether the extent of engagement with the Arena Strive platform predicts better outcomes on the primary measures.
- We will use multilevel-modeling (MLM) in R (using the lme4 package) to compare the various indicators of sleep duration and quality, as well as HRV and RHR, across time as a function of participation in the experimental vs. control conditions. We will allow random intercepts and slopes to model the possibility that some individuals will show different baselines and/or larger effects of participation in the experimental condition than others.
- We will also test for dose effects in the experimental condition via a series of MLMs that estimate whether extent of engagement with the Arena Strive platform predicts better sleep performance and recovery.
- Finally, we will estimate a series of regression-based mediational models that test whether the Arena Strive manipulation enhances sleep and recovery, which in turn enhance the primary outcome measures.

Data Management

WHOOP maintains a Member Data Retention & Disposal Policy to govern our data management practices.

All WHOOP member data retained in any WHOOP environment is subject to the WHOOP's access control, information classification, and key management and cryptography policies. When a data subject requests access to their WHOOP member data, WHOOP takes measures to validate the identity of the requestor to ensure the security of the data being provided.

Disposal of WHOOP member data will be carried out in accordance with the contractual agreement between WHOOP and the member. In the absence of any contractual agreement with respect to Personal Data disposal, an automatic script or manual script (for ad-hoc requests) may be requested by a data subject and, after verifying the identity of the requestor, shall be initiated on the WHOOP

Last Updated: 2.24.2023

platform containing WHOOP member data. This activates a deletion of WHOOP member data on the platform, except for those data elements required to satisfy legal and financial retention requirements.

In connection with our research partnerships, WHOOP will only provide member data to our partners in an anonymized, de-identified manner.

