De-identified data from the applications (WHOOP, Arena-Strive) will be shared with the study coordinator and collaborators listed in the application. No identifiers will be shared with any third party persons or services. Should any participant find wearing any device uncomfortable they will be able to not participate in that part of the study. The other aspects of the study (i.e. Arena Strive educational content) will still be available for their use. Hospital employees are potentially vulnerable subjects and will be protected in two ways. First, all specific identifying information will be coded and assigned study number and device serial number. The data that are collected for analysis by the investigators will not necessitate access to any identifiable medical records. The study investigators will be the sole individuals with access to the identity of the specific assigned study numbers. Secondly, the recruitment material and informed consent will clarify that the decision to participate is voluntary and performance during the study is in no way tied to their employment or pay.

Last Updated: 2.24.2023

Individual results will not be shared with any hospital leadership or administration, or with the participant's coworkers or supervisors unless those members are among the study investigators and with the explicit informed consent from the participant. Participants have access to their own personal physiological data via the Arena Strive and WHOOP apps and individual logins to the WHOOP website. Language will be included in the consent document to reflect the importance of provider well-being. Incidental findings may be identified throughout the study, such as identifying stressors that contribute to anxiety or depression. These will be handled appropriately, with recommendations and resources for professional help. At any point, the participant may choose not to answer a survey question for any reason.

Benefits of Proposed Research to the Subjects and Others (significance of your study)

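### The t-tests for PFI, MBI and Self Valuation name no score, visit or onboarding adjustment; adjusting for the scheduled onboarding score would be more precise at any plausible correlation

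*Combined protocol and SAP*

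**What the plan says.** The table under Data Collection lists PFI, MBI and the Self Valuation Scale as self-reported primary outcomes, each with onboarding, midpoint and exit surveys. Study design gives the times: "once at intervention start, again at week 6 following the first phase of the Arena Strive intervention, then again at week 12". It adds: "Participants in the control cohort will follow this same time frame with respect to self-reported surveys". So each scale has an onboarding score and two candidate follow-up scores in both arms.

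The only direct between-arm comparison named for these scales, in Data Analysis, is: "We will use t-tests in SPSS to compare the primary outcome measures across the experimental and control groups". No score type, visit or covariate follows. The multilevel models in the same section serve "to compare the various indicators of sleep duration and quality, as well as HRV and RHR, across time", so they do not cover the questionnaires. The section also plans "regression-based mediational models that test whether the Arena Strive manipulation enhances sleep and recovery, which in turn enhance the primary outcome measures"; these models reach the scales but name no onboarding adjustment.

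The Objectives summarise the endpoint as: "Primary outcome: Increases in physiological and self-reported measures of resilience / decreases in burnout measures". That points towards change scores but fixes neither score nor visit. On size, Study Participants says: "The maximum number of subjects sought for this study is 100; with a 2:1 randomization ratio".

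**The concern.** Two things are left open. The first is which number is compared. Exit and change scores at week 6 or week 12 give four possible t-tests per scale, and these differ in power. The second is that the onboarding score, which is already scheduled, has no stated use as a covariate. An exit-score t-test ignores it. A change-score t-test subtracts it with a fixed weight of 1, whatever its correlation with the outcome. With at most 100 people and about 33 controls, precision given away here is hard to recover elsewhere.

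**Working it through.** **Inputs.** From the documents: at most 100 people, 2:1, taken as 67 versus 33. The documents contain no sample-size calculation, so there is no planned power figure to reproduce. Assumed, because the documents give none: two-sided alpha 0.05, true effect 0.5 SD, equal SDs at both visits, and a baseline-outcome correlation (rho) over a range.

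**Formulas.** The standard error of an exit-score difference, in SD units, is sqrt(1/67 + 1/33) = 0.2127. Relative to that, the variance of the estimated difference is:

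- exit score: 1
- change score: 2(1 − rho)
- ANCOVA: (1 − rho²) × (1 + 1/(N − 4)). With N = 100 the last factor is 1 + 1/96 = 1.0104, the price of estimating the slope.

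Power comes from the noncentral t distribution, with 98 degrees of freedom for the t-tests and 97 for ANCOVA.

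| rho | Variance: change | Variance: ANCOVA | Power: exit | Power: change | Power: ANCOVA |
|---|---|---|---|---|---|
| 0.3 | 1.400 | 0.919 | 64.4% | 50.3% | 68.0% |
| 0.5 | 1.000 | 0.758 | 64.4% | 64.4% | 76.2% |
| 0.7 | 0.600 | 0.515 | 64.4% | 85.2% | 90.0% |
| 0.8 | 0.400 | 0.364 | 64.4% | 95.7% | 97.1% |

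**Gain from ANCOVA, in points.** Over change scores: 17.7, 11.8, 4.8 and 1.4. Over exit scores: 3.6, 11.8, 25.6 and 32.7.

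**Effect of the unstated score alone.** At rho 0.8, change versus exit is 95.7 − 64.4 = 31.3 points. At rho 0.3 the order reverses: 64.4 − 50.3 = 14.1 points.

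**Where ANCOVA stops winning.** Against the exit score, (1 − rho²) × 1.0104 = 1 gives rho = 0.10. Against the change score, rho = 2/1.0104 − 1 = 0.98. At rho = 0 the loss is about 1% of variance.

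**Smaller analysed samples.** At rho 0.5, exit and change scores have equal power. With 53 versus 27, ANCOVA raises it from 55.1% to 66.8%. With 40 versus 20, it rises from 43.5% to 53.8%.

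**Choice of score after seeing the data.** In simulations under the null (40,000 trials per setting), each single test rejected about 5% of the time. Taking whichever of exit or change at week 12 was significant rejected 8.6–9.6% per scale (rho 0.2–0.8). Opening week 6 as well gave about 13–16% (rho 0.3–0.8).

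**Missing onboarding scores.** Suppose 10% are missing at random (7 of 67 and 3 of 33; assumed). Power at rho 0.2/0.3/0.5/0.7/0.8 is then:

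- exit t-test on all 100: about 64% throughout
- complete-case change t-test: 42/46/60/81/94%
- complete-case ANCOVA: 61/63/72/87/96%
- ANCOVA with the pooled onboarding mean imputed: 66/67/75/87/94%, with type I error 4.8–5.2%

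**Onboarding answered after allocation is known.** Suppose allocation or survey mode shifts onboarding scores by 0.2 SD in one arm and the shift does not carry to week 12 (assumed). The bias is 0 for exit scores, −0.2 SD for change scores and −0.2 × rho for ANCOVA, that is −0.10 SD at rho 0.5 and −0.14 SD at rho 0.7. Null rejection at rho 0.5/0.7 was 5% for the exit t-test, 15/23% for change scores and 8/15% for ANCOVA.

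**The case against.** **A t-test is valid, and change scores were evidently meant.** The first part stands: a reader might infer that the planned test is wrong, but a single pre-specified t-test in the randomised set keeps its error rate. On the second part, change is the more natural reading of the Objectives. If so, the gain is modest when the scales are strongly correlated over time: 5 points at rho 0.7 and about 1 at rho 0.8. The 26 to 33 point gains apply only if exit scores were meant. Even then, the plan does not name the score, and the visit stays open under either reading.

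**The false-positive figures describe an analyst who picks the significant result.** This stands. A reader might infer that the plan runs at 9% per scale, but nothing in the documents says the score will be chosen that way. The figure is a worst case that the silence allows.

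**Adjustment needs a clean baseline.** This is the strongest objection, and it stands as a condition on the remedy. The first survey is placed at the start of the intervention, in-app for one arm and on Typeform for the other, and its order relative to randomisation is not stated. If answers shift with allocation or survey mode, ANCOVA is biased and the exit-score t-test is not. Change scores are biased more, so the objection does not rescue that reading of the plan.

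**Onboarding answers may be missing.** The section on risks and ethics says "the participant may choose not to answer a survey question for any reason". Complete-case ANCOVA can then fall slightly below the exit-score t-test at low rho (61% against 64% at rho 0.2), so a reader should not infer that adjustment always wins. Pooled-mean imputation is not uniformly best either: at rho 0.8 it gives 94% against 96% for complete cases.

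**Conclusion.** The point holds as a specification gap with a nearly free gain in precision. It is not an error that invalidates the comparison. For three primary scales the plan leaves score, visit and onboarding adjustment unstated. Under the stated assumptions the unstated score alone can move power by up to 31 points, and ANCOVA is the most precise of the three options for rho from about 0.10 to 0.98, given onboarding scores. That range covers any plausible value for the same scale repeated 6 to 12 weeks apart.

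The direction is firm. The sizes rest on the assumed effect, alpha, equal SDs, rho and the maximum sample, none of which except the last is in the documents. The recommendation depends on an onboarding score unaffected by allocation and survey mode, and on a rule for missing ones. The per protocol analysis set is a separate matter and is not part of this point.

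**What to change.** In Data Analysis:

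1. Name the week-12 score as the outcome for PFI, MBI and Self Valuation.
2. Replace the t-tests with ANCOVA of the week-12 score on arm and onboarding score. An acceptable alternative is a mixed model of weeks 6 and 12 with arm, visit, arm-by-visit and onboarding score, with the contrast at week 12.
3. State that the onboarding survey is completed before allocation is known, preferably in the same format in both arms. If this cannot be confirmed, report the unadjusted week-12 comparison as a sensitivity analysis.
4. State a rule that keeps people with a missing onboarding score, for example imputing the onboarding mean pooled across arms. This assumes that missingness does not differ by arm, so report onboarding completion by arm.
5. Include the onboarding score in the mediation models for these scales.

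The cost is SAP wording plus a check of when onboarding happens relative to randomisation. If it turns out to follow allocation, moving the survey would be an operational change. No new instrument, visit or software is needed: the onboarding scores are scheduled in both arms, and SPSS and R are already named.

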Last Updated: 2.24.2023

Phase 1: Enrollment period and participant recruitment, obtain informed consent, complete WHOOP device setup & download Arena Strive app. During the study kickoff, intervention participants can choose to attend coaching workshops with an Arena labs performance coach to learn more about the principles of high-performance medicine, biometric data, and the Arena Strive platform.

Phase 2: In the second phase, a performance coaching platform comprising educational content; data feedback and monitoring; and tailored coaching touchpoints will then be administered via the smartphone application, Arena Strive for a duration of 6 weeks (Arena Strive :: Foundations).Arena Labs performance coaches can be accessed via the app. Arena Labs performance coaches provide personalized coaching tailored to the individual clinician and his/ her unique set of needs. The intervention will also include a wearable biometric device provided by WHOOP to collect physiological data relating to measures of resilience and autonomic function. The accompanying WHOOP app will be available in this phase of the intervention. Data from the wearable device will be passed directly into the Arena Strive app to be summarized and delivered to participants through the app interface for self-monitoring, feedback, and coaching touchpoints.

Phase 3: After 6 weeks of asynchronous guidance through the Arena Strive app, users will then continue the intervention (Arena Strive :: Explorations) with an additional 6 week experience of data feedback.

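### The dose analysis relates self-chosen engagement to outcome within one arm and specifies no baseline adjustment, so starting level alone can create, hide or reverse an apparent dose effect

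*Combined protocol and SAP*

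**What the plan says.** The Data Analysis section has two dose bullets, both confined to the experimental arm.

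- **Primary measures.** The plan will "test for dose effects in the experimental condition via a series of correlational analyses" and asks whether the "extent of engagement with the Arena Strive platform predicts better outcomes on the primary measures".
- **Sleep and recovery.** The plan will "test for dose effects in the experimental condition via a series of MLMs that estimate whether extent of engagement" predicts better results.

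Neither bullet names a baseline term, a change score, a covariate, an engagement metric, a time order or an exploratory label. Random intercepts and slopes are mentioned only in the bullet comparing the two randomised groups.

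Engagement is app use logged during the intervention: "videos/audio watched or listened to, content favorited, or user activities completed" (Study design). Part of the coaching contact is optional: "intervention participants can choose to attend coaching workshops with an Arena labs performance coach" (Intervention, Phase 1).

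A baseline exists. Study design schedules the surveys "once at intervention start, again at week 6 following the first phase of the Arena Strive intervention", with a last one at week 12. The Data Collection table lists the Professional Fulfillment Index (PFI), the Maslach Burnout Inventory (MBI) and the Self Valuation Scale under "Onboard, midpoint, and exit Survey".

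**The concern.** Within the experimental arm nobody is randomised to a level of engagement. Clinicians who start with less burnout or lighter schedules may use the app more, and those who start worse off may also use it more. In either case engagement carries information about starting level. Starting level predicts the week-12 score whether or not the platform works. A correlation that leaves it out mixes the two, and calling the result a dose effect gives it a causal name.

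Reverse causation is also possible. Under Phase 2 of the Intervention section, the wearable's data are fed back to participants in the app, so a change in sleep or heart rate variability can change how much someone engages.

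At stake is the reading of a supporting analysis. The section on benefits already cites larger gains among highly engaged users as a benefit of the platform, so an association of this kind could be read as support for efficacy.

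**Working it through.** The plan gives no power, alpha, standard deviation or correlation, so there is no stated figure to reproduce.

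**Inputs from the documents**
- Total: "The maximum number of subjects sought for this study is 100" (Study Participants), allocated 2:1. Experimental arm at that maximum: 100 × 2/3 ≈ 67.

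**Assumed inputs**
- Two-sided alpha of 0.05.
- No platform effect, and all scores oriented so that higher is better.
- a = correlation of engagement with the baseline score: 0 to 0.4, and its mirror image below zero.
- ρ = correlation of the baseline with the week-12 score: 0.5 to 0.7.
- 20% loss as a sensitivity case: 67 × 0.8 ≈ 54.

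**Step 1: induced correlation.** If baseline is the only common cause, r = a × ρ.
- a = 0: r = 0
- 0.2 × 0.5 = 0.10
- 0.3 × 0.6 = 0.18
- 0.4 × 0.7 = 0.28

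**Step 2: rejection rate.** By Fisher's z, the test statistic has mean atanh(r) × √(n − 3). With n = 67, √64 = 8.

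| r | mean of z | rejection rate |
|---|---|---|
| 0 | 0 | 5% |
| 0.10 | 0.1003 × 8 = 0.80 | 12.6% |
| 0.18 | 0.1820 × 8 = 1.46 | 30.7% |
| 0.28 | 0.2877 × 8 = 2.30 | 63.4% |

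Simulation of the Pearson test (20,000 replicates per case) gives 13.1%, 30.9% and 64.1% for the last three rows. With n = 54 the middle case gives 26%.

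**Step 3: negative a.** The sign flips and the two-sided rate is the same. With a = −0.3 and ρ = 0.6, r = −0.18 and a false harmful dose effect appears 31% of the time. A true association of +0.18 would be roughly cancelled.

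**Step 4: would a change score help?** The induced correlation becomes −a × √((1 − ρ)/2). For a = 0.3 and ρ = 0.6 this is −0.3 × √0.2 = −0.13, with 19% rejection. The bias reverses sign but remains.

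**Step 5: baseline adjustment.** The partial correlation given baseline rejects 4.8% to 5.4% of the time in every case run, if baseline is the only common cause. Now add an unmeasured cause that loads 0.2, 0.3 or 0.4 on both engagement and outcome (a = 0.3, ρ = 0.6). The adjusted test then rejects 7%, 16% or 39% of the time.

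**Step 6: should the week-6 score be a covariate too?** It is taken after engagement in weeks 1–6, so it can carry that engagement's effect. Suppose a stable trait has variance 0.6, occasion noise has variance 0.4, and a true effect of 0.3 is present at both week 6 and week 12.
- Given the onboard score, the remaining trait variance is 0.6 × 0.4 = 0.24.
- The week-6 coefficient is then 0.24/(0.24 + 0.40) = 0.375.
- The engagement coefficient falls from 0.30 to 0.30 × (1 − 0.375) = 0.19.
- If week 12 depends on the past only through week 6, it falls to zero.

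**Scope.** The Data Collection table lists 12 primary measures: 3 survey instruments and 9 biometrics. Sleep and recovery have their own dose bullet, and the mediation bullet sets sleep and recovery apart from the primary outcome measures. The correlations are therefore best read as covering PFI, MBI and Self Valuation. The rates above are for a correlation test and do not describe the multilevel models, which the plan specifies too briefly for a comparable figure.

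**The case against.** The strongest reply is that this is one sentence about a supplementary analysis. The randomised comparison comes first, no success rule depends on the dose results, and the text does not rule out adjustment. The size of the bias rests wholly on correlations that the documents do not give, and if engagement is unrelated to starting level the test is valid. All of this stands, and it limits what can be claimed.

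A reader might infer four stronger things, none of which the documents support:

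- **That the plan commits to unadjusted correlations.** It is silent. The supportable statement is that no adjustment is specified.
- **That the problem recurs over all 12 primary measures at the rates shown.** Nine are biometrics, whose sleep and recovery dose effects go to separate models.
- **That the bias must flatter the platform.** Its direction is unknown. The protocol says the program also helps people already burnt out, so those who start worse may engage more.
- **That the trial's efficacy result is compromised.** The comparison between randomised groups does not use engagement.

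What survives is that nothing in the plan requires the analyst to use the onboard scores, and the result is called a dose effect without any caveat.

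**Conclusion.** The concern holds in a limited form. As specified, the survey-instrument correlations cannot separate an effect of engagement from a difference in starting level. The false-positive rate runs from 5%, when the two are unrelated, to about 63% at the upper end of the assumed range, with 31% in the middle case. With negative correlations the error runs against the platform. These rates assume no platform effect, a two-sided 5% test, the full arm of 67 and baseline as the only common cause.

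For the sleep and recovery models the concern is qualitative: a random intercept alone does not stop person-level engagement from picking up differences between people. Even after adjustment, both analyses remain exploratory. The change is worth making before analysis.

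**What to change.** **Survey instruments.** Replace the correlations with a linear regression of the week-12 score on one engagement metric defined in advance, adjusted for the onboard score of the same measure.
- If the exposure is engagement in weeks 1–6, do not adjust for the week-6 score.
- Use the week-6 score as the baseline only when the exposure is engagement in weeks 7–12.
- Add role and department only if they are recorded. They appear as eligibility and setting facts, not in the Data Collection table.

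**Multilevel dose models.** Enter each person's mean engagement (between-person) and the deviation from that mean (within-person) as separate terms, taking engagement from the period before the outcome.

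**Label.** Report both as an exploratory association of engagement with outcome. State that engagement was not randomised, that unmeasured confounding remains, and that the result is neither a dose effect nor evidence of efficacy.

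**Cost.** A revised paragraph in the plan, a little more analysis work to build the engagement metric and its lagged form, and a less favourable label. Onboard scores and app engagement are already collected.
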